15. APPENDICES

Appendix A. Schedule of Assessments – Part A

Study Period (or Dose #)	Screen	Lead-In		Dose 1		Dose 2	Dose 3	Dose 4	Dose 5	Dose 6	Dose 7	Dose 8
Study Week	≤ 42 days		Baseline Visit	1		2	3	4	5	6	7	8
Study Day		2 to 4 Weeks	Day -8/-7 to Day -2/-1	Pre-dose	1	8 ± 1	15 ± 1	22 ± 1	29 ± 1	36 ± 1	43 ± 1	50 ± 1
Informed consent	X											
Medical History ^a	X		X									
Physical examination	X		X						X			
Height (Screening only) & Body weight	X	X	X						X			
Urine pregnancy test (women); FSH ^g	X		X						X			
Urine drug/alcohol test	X		X						X			
12-lead ECG ^b	X		X						X			
Vitals (BP, RR, HR, T) ^c	X	X	X	X		X	X	X	X	X	X	X
Chemistry, Hematology, Lipid Panel, and Urinalysis	X		X			X	X		X		X	
Fasting (≥ 8-hr) plasma glucose ^e			X	X		X	X	X	X	X	X	X
Serum Ketones & Free Fatty Acids			X	X		X	X	X	X	X	X	X
Study Drug SC Administration					X	X	X	X	X	X	X	X
Seven-point blood glucose profile ^d		X						X				X
Unblinded Continuous Glucose Monitoring (CGM) ^h		X										
Ketone finger-stick ^j					X	X	X	X	X	X	X	X
Daily insulin usage dairy ⁱ		X			X	X	X	X	X			X
Hourly plasma glucose via YSI ^e			X ¹									
Mixed Meal Tolerance Test (MMTT) ^e			X									
Arginine Challenge Test ^e			X ¹									
HbA1c	X		X									
Insulin, C-peptide, GLP-1, and Glucagon ^{e,f}			X						X			
Serum PK sample collection ^f				X		X			X			
Anti-REMD-477 Ab sample collection ^f				X								
Exploratory biomarker collection				X								
QOL Questionnaires ^k			X									
Overnight Admission ^l			X									
Con-Med monitoring	X											
Adverse event monitoring												

Footnote Key:

- a. Medical history includes significant past medical events (e.g. prior hospitalizations or surgeries), a review of diabetes history and glycemic control, and any concurrent medical illnesses.
- b. After the Screening Visit, 12-lead ECG to be performed in triplicate, approximately 1 min apart. When ECG and blood sample collection occur at the same time, ECGs should be performed before blood samples are drawn.
- c. Vital signs include blood pressure, respiratory rate, heart rate, and oral temperature.
- d. Seven-point blood glucose profile will measure glucose by finger stick over three consecutive days before and 2 hours after each meal, and at bedtime.
- e. **For a subset of subjects enrolled prior to Protocol Amendment #1:** subjects should fast overnight for 8 hours prior to MMTT. During the overnight fast, plasma glucose via YSI will be measured hourly, and subjects will be allowed to receive juice by mouth, in case of hypoglycemia. For the Overnight Baseline Visit (OBV), Day 85 visit and Day 162 Visit, fasting plasma glucose samples will be collected on the morning following admission, prior to the administration of the MMTT and Arginine Challenge Tests. MMTT must be completed prior to the Arginine Challenge Test.

For ongoing or newly enrolled subjects at the time of Protocol Amendment #1: overnight admission to the CRU at Baseline, Week 13, and Week 24 will not occur. For these visits, subjects will still return to the CRU to complete all the study procedures outlined here in the Schedule of Assessments table – however, all assessments for that visit will be performed on a single day (*Baseline Visit: Day -8 to Day -1; Week 13 Visit: performed on Day 85; and Week 24 Visit: performed on Day 162*).

- **Note:** For ongoing or newly enrolled subjects at the time of Protocol Amendment #1, the MMTT will only be administered at the Baseline and Week 13 visits, after the subject completes an 8 hour overnight fast at home (the MMTT is no longer required at Week 24). No Arginine Challenge Tests or YSI assessments will be performed for these subjects.
- f. Sample should be collected pre-dose on all dosing days.
- g. FSH required at screening for post-menopausal women.
- h. Unblinded CGM will be performed for two weeks during the Lead-in Period (completed prior to the OBV), and throughout the study Dosing and Follow-up Periods from Dose 1 through the End of Study Visit. For on-going or newly enrolled subjects in Part A at the time of Protocol Amendment #2, CGM data will be collected throughout the study from Dose 1 through the Day 85/Week 13 Visit, and CGM devices will be “unblinded”. CGM data will be downloaded at the clinical research unit during scheduled site visits, as indicated in the Schedule of Assessments.
- i. Subjects will be given insulin usage diaries during the Lead-in Period and at the beginning of Weeks 1 through 4, 8, 12, 16, and 20. For both weeks of the Lead-in Period and Weeks 1 through 4, daily insulin use (short-acting, long-acting, and infusional as applicable) will be collected over seven days. For Weeks 8, 12, 16, and 20, daily insulin will be collected over a period of 3 consecutive days within that respective week.
- j. Blood ketones will be measured in the morning (prior to the subject's morning meal) 3 days a week – on an alternate day basis (e.g. Week 1: Study days 1, 3, and 5 or on Mondays, Wednesday, and Fridays) during the 12-Week Dosing Period (starting on Day 1 and continuing through the completion of Week 12), and once weekly throughout the Follow-up Period & EOS (Day 85 through Day 162) via finger-stick (strips for finger-stick measurement will be provided to the subjects). Subjects will be instructed to contact the investigator if they have positive ketones.
- k. The *WHO-5 Well-Being Index & T1-DDS* QOL Questionnaires will be completed by the subjects at the OBV, Day 84, and Day 161.
- l. No longer applicable for ongoing or newly enrolled subjects at time of Protocol Amendment #1.

Schedule of Assessments – Part A

Study Period (or Dose#)	Dose 9	Dose 10	Dose 11	Dose 12	Follow-up Period			EOS					
Study Week	9	10	11	12	13 ^m	16	20	24 ^m					
Study Day	57 ± 1	64 ± 1	71 ± 1	78 ± 1	84 ± 2	85 ± 2	106 ± 2	134 ± 2	161 ± 2	162 ± 2			
Informed consent													
Medical History ^a													
Physical examination					X				X				
Body weight	X				X	X	X		X				
Urine pregnancy test (women); FSH ^g	X				X				X				
Urine drug/alcohol test									X				
12-lead ECG ^b	X		X			X			X				
Vitals (BP, RR, HR, T) ^c	X	X	X	X	X	X	X	X	X				
Chemistry, Hematology, Lipid Panel, and Urinalysis	X					X			X				
Fasting (\geq 8-hr) plasma glucose ^e	X	X	X	X		X			X				
Serum Ketones & Free Fatty Acids	X	X	X	X		X	X						
Study Drug SC Administration	X	X	X	X									
Seven-point blood glucose profile ^d				X			X	X					
Unblinded Continuous Glucose Monitoring (CGM) ^h	↔												
Daily (or Weekly) Ketone finger-stick ^j	X	X	X	X		X	X						
Daily insulin usage diary ⁱ				X		X	X						
Hourly plasma glucose via YSI ^e					X ¹	X ¹		X ¹	X ¹				
Mixed Meal Tolerance Test (MMTT) ^e						X			X ¹				
Arginine Challenge Test ^e						X ¹			X ¹				
HbA1c						X			X				
Insulin, C-peptide, GLP-1, and Glucagon ^{e,f}	X					X	X		X				
Serum PK sample collection ^f	X					X	X						
Anti-REMD-477 Ab sample collection ^f						X			X				
Exploratory biomarker collection						X			X				
QOL Questionnaires ^k					X				X				
Overnight Admission ^l					↔			↔					
Con-Med monitoring	↔												
Adverse event monitoring	↔												

Footnote Key:

- a. Medical history includes significant past medical events (e.g., prior hospitalizations or surgeries), a review of diabetes history and glycemic control, and any concurrent medical illnesses.
- b. After the Screening Visit, 12-lead ECG to be performed in triplicate, approximately 1 min apart. When ECG and blood sample collection occur at the same time, ECGs should be performed before blood samples are drawn.
- c. Vital signs include blood pressure, respiratory rate, heart rate, and oral temperature.
- d. Seven-point blood glucose profile will measure glucose by finger stick over three consecutive days before and 2 hours after each meal, and at bedtime.
- e. **For a subset of subjects enrolled prior to Protocol Amendment #1:** subjects should fast overnight for 8 hours prior to the MMTT. During the overnight fast, plasma glucose via YSI will be measured hourly, and subjects will be allowed to receive juice by mouth, in case of hypoglycemia. For the Overnight Baseline Visit (OBV), Day 85 visit and Day 162 Visit, fasting plasma glucose samples will be collected on the morning following admission, prior to the administration of the MMTT and Arginine Challenge Tests. MMTT must be completed prior to the Arginine Challenge Test.

For ongoing or newly enrolled subjects at the time of Protocol Amendment #1: overnight admission to the CRU at Baseline, Week 13, and Week 24 will not occur. For these visits, subjects will still return to the CRU to complete all the study procedures outlined in the Schedule of Assessment table – however, all assessments for that visit will be performed on a single day (*Baseline Visit: Day -8 to Day -1; Week 13 Visit: performed on Day 85; and Week 24 Visit: performed on Day 162*).

- **Note:** For ongoing or newly enrolled subjects at the time of Protocol Amendment #1, the MMTT will only be administered at the Baseline and Week 13 visits, after the subject completes an 8 hour overnight fast at home (the MMTT is no longer required at Week 24). No Arginine Challenge Tests or YSI assessments will be performed for these subjects.
- f. Sample should be collected pre-dose on dosing days.
- g. FSH required at screening for post-menopausal women.
- h. Unblinded CGM will be performed for two weeks during the Lead-in Period (completed prior to the OBV), and throughout the study Dosing and Follow-up Periods from Dose 1 through the End of Study Visit. For on-going or newly enrolled subjects in Part A at the time of Protocol Amendment #2, CGM data will be collected throughout the study from Dose 1 through the Day 85/Week 13 Visit, and CGM devices will be “unblinded”. CGM data will be downloaded at the clinical research unit during scheduled site visits, as indicated in the Schedule of Assessments.
- i. Subjects will be given insulin usage diaries during the Lead-in Period and at the beginning of Weeks 1 through 4, 8, 12, 16, and 20. For both weeks of the Lead-in Period and Weeks 1 through 4, daily insulin use (short-acting, long-acting, and infusional as applicable) will be collected over seven days. For Weeks 8, 12, 16, and 20, daily insulin will be collected over a period of 3 consecutive days within that respective week.
- j. Blood ketones will be measured in the morning (prior to the subject's morning meal) 3 days a week – on an alternate day basis (e.g. Week 1: Study days 1, 3, and 5 or on Mondays, Wednesday, and Fridays) during the 12-Week Dosing Period (starting on Day 1 and continuing through the completion of Week 12), and once weekly throughout the Follow-up Period & EOS (Day 85 through Day 162) via finger-stick (strips for finger-stick measurement will be provided to the subjects). Subjects will be instructed to contact the investigator if they have positive ketones.
- k. The *WHO-5 Well-Being Index & T1-DDS QOL* Questionnaires will be completed by the subjects at the OBV, Day 84, and Day 161.
- l. No longer applicable for ongoing or newly enrolled subjects at time of the Protocol Amendment #1.
- m. **For ongoing or newly enrolled subjects at time of the Protocol Amendment #1:** overnight admission to the CRU at Week 13 & Week 24 will not occur.

For these visits, Week 13 procedures will be performed on Day 85, and Week 24 procedures will be performed on Day 162.

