no significant drug related adverse events. No deaths, dose limiting toxicities or withdrawals due to adverse events have been reported. No notable changes in ECG, safety lab tests, or vital signs were reported. One patient whose treatment assignment remains blinded experienced an increase in ALT that was less than 1.6 times the upper limit of the laboratory normal on Days 22 and 50 after a single SC injection. There was no corresponding increase in bilirubin or alkaline phosphatase. The elevation occurred 21 and 49 days after administration of treatment which is not consistent with previous observations for liver enzyme increases in both healthy subjects and Type 2 diabetics which usually occur between 4-14 days after drug administration. No severe hypoglycemia was reported in the study patients.

An interim analysis of the first 17 subjects found REMD-477 treatment reduced daily insulin use by 32% (4.2%, 60%) vs. placebo on Day 4 ($p=0.027$). Average daily glucose assessed by CGM was 19 mg/dL (6.2, 31; $p=0.006$), and 26 mg/dL (8.2, 45; $p=0.008$) lower in the REMD-477 group than in the placebo group at Weeks 2 and 3 after treatment, respectively. Glucose time-in-range (70-180 mg/dL) for REMD-477 was 9.5% (2.7%, 16%; $p=0.009$) and 13% (1.9%, 25%; $p=0.026$) greater in the REMD-477 group than in the placebo group during Weeks 2 and 3 after treatment, respectively.

Phase-1b-2a Study T2DM: R477-201

Protocol R477-201 is a randomized, placebo-controlled, double-blind, dose escalation study to evaluate safety, tolerability, PK and PD of single and repeated SC doses of REMD-477 in Type 2 diabetic subjects. The ongoing study includes a dose escalation phase (Part A) followed by an adaptive dose cohort phase (Part B) and two additional cohorts testing REMD-477 in combination with metformin (Part C).

In Parts A and B, approximately 72 subjects will be enrolled with Type 2 diabetes who are either treatment-naïve, controlled with diet and exercise or treated with oral antidiabetic medications. As of February 2017, 60 of subjects have been enrolled across 5 dose cohorts at dose levels of 14 mg, 28 mg, 35 mg, 42 mg, and 70 mg. Each cohort included 9 patients treated with REMD-477 and 3 treated with placebo. Patient received a single SC injection and 28 day observation followed by 8 weekly SC injections.

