Part C of this study will enroll approximately 30 subjects with Type 2 diabetes who are currently on stable doses of metformin for at least 8 weeks. Each cohort will include 10 patients treated with REMD-477 and 5 treated with placebo. Patients will receive 12 weekly SC injections.

As of March 2017, the safety and tolerability of REMD-477 (multiple doses up to 70 mg SC) is available in 48 patients with T2DM. There are no significant drug related adverse events. No deaths, dose limiting toxicities or withdrawals due to adverse events have been reported. No notable changes in ECG or vital signs were reported. Importantly, there was no evidence of increased blood pressure. Mild reversible elevations of ALT up to 2.5x ULN were observed in 2 of 12 patients in the 42 mg cohort. At 70 mg, ALT increases up to 3x ULN were observed in 7 of 12 patients in the 70 mg cohort with a single isolated elevation of 18x ULN in one patient at one time-point that decreased below the ULN with continued dosing. Transaminase elevations were not associated with bilirubin or alkaline phosphatase increases. There were no other notable safety lab abnormalities observed. No hypoglycemia was observed across all dose cohorts.

Based on preliminary analysis, fasting glucose decreased 45-52 mg/dL relative to baseline after multiple doses of 14 mg to 42 mg while placebo treatment was associated with a decrease up to 10 mg/dL. Glucose AUC also decreased 130-172 h*mg/dL relative to baseline in the REMD-477 group versus placebo which showed decreases up to 39 h*mg/dL. HbA1c was evaluated at Days 57, 85, and 141 and showed a maximum decrease of 0.28%, 0.58%, and 1% for 14, 28, and 42 mg groups, respectively versus an increase of 0.03% for the placebo group.

Phase-1 b-2a Study T2DM: REMD-477-201 – Clinical Pharmacokinetics

Detailed plasma concentration over time profiles for REMD-477 were obtained at dose levels between 14 mg and 70 mg after the first and last SC injection. Consistent with results in healthy subjects (FIH Study 20060310), exposure, as assessed by C_{max} and AUC_{0-inf} , increased more than dose-proportionally between the 14 mg and 70 mg dose range. The effective half-life after single and multiple dosing was approximately 1 week across dose groups. Geometric mean accumulation ratio values were 11.2, 29.8, and 12.7 at the 14-, 28-, and 42-mg dose levels, respectively, indicating significant accumulation of REMD-477 after multiple dosing.

Dose Selection Rationale

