The proposed dose design for the current study is for subjects to be randomized in a 1:1:1 fashion into one of three treatment groups (placebo, 35 mg REMD-477, or 70 mg REMD-477). Subjects will receive once weekly SC injections of investigational product for 12 weeks and be followed for an additional 12 weeks during washout in the Safety Follow-up Period. In

the subjects with Type 2 diabetes, increasing dose and exposure from 14 mg to 42 mg was associated with reduction in HbA1c. Based on available unblinded interim data, the maximum HbA1c reduction of 1% was achieved at 42 mg after 8 repeated weekly doses. In a blinded evaluation of the 70 mg cohort safety data, ALT increases were observed in a greater number of subjects relative to previous lower dose cohorts. In contrast, a single SC dose of 70 mg REMD-477 was not associated with significant increases in ALT in subjects with Type 1 diabetes. Only one subject who received blinded treatment had elevated ALT that were up to 1.6x ULN.

After a single dose of 70 mg of REMD-477 in subjects with Type 1 diabetes, significant reductions in insulin, average glucose, and time in range after CGM were observed. With repeated weekly dosing, substantial (10-30x) accumulation of REMD-477 is expected.

Based on the above findings, dose levels of 35 mg and 70 mg administered once weekly by SC injection over 12 weeks are being proposed. At these dose levels, significant improvements in glycemic control and reduction in insulin requirements are expected after multiple dosing. In addition, minimal to no transaminase elevations are expected based on the findings in Type 1 diabetics after a single 70 mg dose and the manageable transaminase elevations in Type 2 diabetics.

Hypothesis

Multiple doses of REMD-477 will significantly decrease daily insulin use versus placebo treatment at Week 12.

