Fasting Plasma Glucose	2	15	30
Fasting Lipid Panel	5	9	45
Serum PK sample collection	4	6	24
Serum FSH levels (women only) ^Φ	5	1	5 ^Φ
HbA1c	6	4	24
Plasma Glucose via YSI	NA	NA	NA
MMTT (glucose & insulin)	40	2	80
GLP-1 (active & total), Glucagon, Plasma insulin and C-peptide	4	6	24
Anti-REMD-477 Ab sample collection *	10 (first) / 5	3	20
Exploratory biomarker collection	30	3	90
Serum Ketones & free fatty acids	1.5	15	22.5
TOTAL**			404.5 409.5^Φ

* First collection is 10 mL, subsequent collections are 5 mL.

** Volume to be collected over approximately 238 days.

Table 7-3: Total Blood Volume for samples collected under Protocol Amendment #2, for subjects participating in Part B

Procedure	Volume per Collection (mL)	Number of Collections	Total Volume (mL)
Safety (chemistry + hematology)	5	9	45
Fasting Plasma Glucose	2	15	30
Fasting Lipid Panel	5	9	45
Serum PK sample collection	4	6	24
Serum FSH levels (women only) ^Φ	5	1	5 ^Φ
HbA1c	6	5	30
GLP-1 (active & total), Glucagon, Plasma insulin and C-peptide	4	6	24
Anti-REMD-477 Ab sample collection *	10 (first) / 5	3	20
Exploratory biomarker collection	30	3	90
Serum Ketones & free fatty acids	1.5	15	22.5
Liver Injury Biomarkers	10	5	50
TOTAL**			380.5 385.5^Φ

* First collection is 10 mL, subsequent collections are 5 mL.

** Volume to be collected over approximately 224 days.

Laboratory Safety Tests

Blood and urine samples for laboratory safety tests (clinical chemistry, hematology, and urinalysis) will be collected according to the Schedule of Assessments ([Appendix A](#)).

The date and time of blood and urine collection will be recorded in the subject's source documentation. The tests will be analyzed using standard procedures. White blood cell differentials will be reported in absolute counts.

All laboratory tests must be reviewed by the Principal Investigator or qualified designee prior to the subject receiving each dose. Additional safety laboratory assessments may be performed if clinically indicated.

The following analytes will be tested:

Chemistry

Albumin	Blood urea nitrogen (BUN)
Calcium	Chloride
Glucose	Phosphorus
Potassium	Serum creatinine
Magnesium	Sodium
Bicarbonate	Uric acid
Aspartate aminotransferase (AST)	Alanine aminotransferase (ALT)
Cholesterol	Lactate dehydrogenase (LDH)
Alkaline phosphatase (ALP)	Total bilirubin
Total protein	Direct bilirubin
HDL, LDL, Triglycerides	Total globulin

Hematology

Red blood cells (RBC)
Hemoglobin (Hgb)
Hematocrit (Hct)
Mean corpuscular volume (MCV)

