- d. Seven-point blood glucose profile will measure glucose by finger stick over three consecutive days before and 2 hours after each meal, and at bedtime.
- e. Sample should be collected pre-dose on all dosing days.
- f. FSH required at screening for post-menopausal women.
- g. Blinded CGM will be performed for one week during the Lead-in Period (completed prior to the Baseline Visit), and for one week after Doses 1, 4, 8 and 12. CGM data will be downloaded at the clinical research unit during scheduled site visits, as indicated in the Schedule of Assessments.
- h. Subjects will be given insulin usage diaries during the Lead-in Period and at the beginning of Weeks 1 through 4, 8, 12, 16, and 20. For one week of the Lead-in Period and Weeks 1 through 4, daily insulin use (short-acting, long-acting, and infusional as applicable) will be collected over seven days. For Weeks 8, 12, 16, and 20, daily insulin will be collected over a period of 3 consecutive days within that respective week.
- i. The *WHO-5 Well-Being Index & T1-DDS QOL* Questionnaires will be completed by the subjects at the Baseline, Day 84, and Day 161.
- j. Both the Liver MRI and FibroScan Baseline Assessments may be performed up to 7 days before the Day 1 Visit, after all other inclusion and exclusion criteria have been met.

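### The maximum ALT/AST tables leave out unscheduled results, which the sustained-rise stopping rule depends on; secondarily, no ALT/AST is scheduled between Day 57 and Day 85

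*Protocol*

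**What the plan says.** **Schedule.** In Protocol Appendix A, both Parts carry ALT and AST in one row only, "Chemistry, Hematology, Lipid Panel, and Urinalysis". It is marked at screening, baseline, Days 8, 15, 29, 43, 57 and 85, and end of study. It is blank on Days 64, 71 and 78, the visits for Doses 10 to 12. In Part B a footnote to the row says "Sample should be collected pre-dose on all dosing days". The Part A row has no such footnote, but Protocol Section 7 (Laboratory Safety Tests) says for both Parts that "All laboratory tests must be reviewed by the Principal Investigator or qualified designee prior to the subject receiving each dose". The same section permits extra safety tests when there is a clinical reason.

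**Stopping rules.** Protocol Section 6 makes a subject stop for ALT/AST above 3x ULN together with ALP or bilirubin above 2x ULN, or for three consecutive ALT/AST values above 5x ULN within 14 days.

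**Reporting.** SAP 10.1.2 treats any laboratory result outside a scheduled timepoint as unscheduled. It is labelled in the listings and, unless it serves as baseline, stays out of every summary. (In the SAP, a repeat reading means vital signs or ECG only, so a retested ALT is unscheduled.) SAP 10.4.2 counts subjects whose maximum post-dose ALT or AST exceeds 3x, 5x and 10x ULN, counts them again by timepoint, and tabulates by timepoint ALT/AST >3x with total bilirubin >2x ULN. It says nothing about unscheduled readings. SAP 10.4.4 expressly includes them in the QTc outlier analysis.

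**Background.** In the type 2 study (Protocol Section 2), "Patient received a single SC injection and 28 day observation followed by 8 weekly SC injections". There, "ALT increases up to 3x ULN were observed in 7 of 12 patients in the 70 mg cohort". One patient also had a lone value of 18x ULN, which fell back under the ULN while dosing went on. For type 1 diabetes the protocol reports that "a single SC dose of 70 mg REMD-477 was not associated with significant increases in ALT in subjects with Type 1 diabetes", and says "minimal to no transaminase elevations are expected based on the findings in Type 1 diabetics after a single 70 mg dose".

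**The concern.** ALT is the laboratory signal that the protocol itself reports for this drug, so the ALT/AST threshold tables are where a reader will look for it. A marked value is normally followed by a retest. Under SAP 10.1.2 the retest is unscheduled, so the readings most likely to show the peak, and the readings that trigger a mandatory stop, are the ones the tables omit. The number of subjects above 5x or 10x ULN can then be understated, and a subject withdrawn under the sustained-rise rule need not appear in the tables at the level that caused the withdrawal.

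The schedule adds to this. Spacing between draws doubles over the last weeks of dosing, so a rise that starts after Day 57 and gives no clinical prompt is first seen on schedule at Day 85, when dosing is over. If a clinical prompt does lead to an earlier test, that test is unscheduled and outside the tables.

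**Working it through.** **1. Read the schedule.** Counting the marks gives screening, baseline and seven post-dose draws (8, 15, 29, 43, 57, 85, end of study): 9 collections in each Part. Protocol Tables 7-1, 7-2 and 7-3 also state 9, so the blanks are not a fault of table extraction.

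**2. Can scheduled draws alone satisfy the sustained-rise rule?** Span of three consecutive scheduled post-dose draws = third day − first day:

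- Days 8, 15, 29: 29 − 8 = 21
- Days 15, 29, 43: 28
- Days 29, 43, 57: 28
- Days 43, 57, 85: 42
- Days 57, 85, 162: 105

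None of the 5 is within 14 days. With the ±1-day windows the shortest is (29 − 1) − (8 + 1) = 19. At least one of any three post-dose values within 14 days is therefore unscheduled. Days 1, 8 and 15 in Part B span 14 days, but Day 1 is pre-dose and entry requires ALT and/or AST of at most 1.5x ULN at screening.

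**3. Follow those values into the tables.** Two illustrations:

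- 6x ULN at a scheduled visit and 12x on the retest: the subject counts as >5x but not >10x.
- Three clinically prompted draws between Days 57 and 85, all >5x ULN within 14 days, with ALT and AST below 3x at every scheduled visit: the mandatory stop applies, yet the subject appears in none of the three threshold tables.

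**4. Size of the schedule gap.** 85 − 57 = 28 days; with windows, (85 − 2) − (57 + 1) = 25 to (85 + 2) − (57 − 1) = 31. From Day 15 to Day 57 the spacing is 14 days (12 to 16).

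**5. What this means for each dose.** Age of the newest scheduled result from an earlier visit (a same-day draw is not counted):

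| Dose | 3 | 4 | 5 | 6 | 7 | 8 | 9 | 10 | 11 | 12 |
|---|---|---|---|---|---|---|---|---|---|---|
| Age in days | 7 | 7 | 14 | 7 | 14 | 7 | 14 | 7 | 14 | 21 |

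Only Dose 12 is out of line (78 − 57 = 21). Day 85 is 85 − 78 = 7 days after the last dose and cannot inform dosing.

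**6. Effect of a Day 71 draw.** The gap becomes 14 + 14 days (12 to 16, then 11 to 17 with windows). The age at Dose 12 falls to 78 − 71 = 7. The longest delay from the start of a lasting rise to a scheduled draw falls from 28 to 14 days. Three scheduled draws still never fall within 14 days (0 of 6 triplets), so this does not replace the SAP change. How many brief rises would be missed cannot be computed, because neither document gives their duration.

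**The case against.** **On the tables.** SAP 10.4.2 contrasts a maximum over any post-dose timepoint with counts at each assessment timepoint, and a programmer might take the first to include everything. Exclusion is the likelier reading, because SAP 10.1.2 is general and SAP 10.4.4 shows how an exception is written, but it is not certain. Nor are the values lost. They stay in the listings, out-of-range values are flagged there, and under Protocol Section 9 a laboratory change that needs therapy or a change of therapy is an adverse event. What stands is that the threshold tables themselves can understate the peak.

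**On the stopping rule.** A reader might infer that the rule is unworkable. It is not. A rule needing three values in 14 days is confirmatory, and an abnormal result is expected to prompt extra tests. Its reliance on them matters only because the SAP leaves them out of the tables.

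**On the gap.** A reader might infer that Doses 9 to 12 are given without usable liver data, or that the protocol breaks its own review requirement. Neither holds. Doses 9 to 11 rest on results 7 to 14 days old, as earlier doses do. The requirement is to review tests before each dose, not to draw a new panel each time, and Days 22, 36 and 50 are blank too. Extra tests are allowed on clinical grounds, and the Safety Review Committee reviews data at about 33%, 66% and 100% of Part A.

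A reader might also infer that liver risk concentrates in the gap. The reported type 2 ALT data do come from cohorts given 8 weekly doses, but no text reports rises first appearing after Dose 8. The type 2 rises came without bilirubin or ALP increases, and the type 1 single-dose data are reassuring. What stands is narrower: a clinical prompt may be absent when a rise is silent, and Dose 12 rests on an older result than any of Doses 3 to 11.

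**Conclusion.** The main point holds. As written, SAP 10.1.2 and 10.4.2 together omit from the maximum-value tables at least one qualifying value for every subject who meets the sustained-rise rule, and any peak found only on an unscheduled test. This rests on two assumptions: that SAP 10.1.2 governs where SAP 10.4.2 is silent, and that all three qualifying values are post-dose. The documents give no figure for how many subjects this would affect.

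The schedule point holds as a secondary one: a 28-day gap against 14 days before it, and one dosing decision (Dose 12) made on a 21-day-old scheduled result instead of one at most 14 days old. An earlier draw would not by itself force a stop for an isolated rise. It would do so only if ALP or bilirubin also exceeded 2x ULN. Otherwise it would allow retesting and a discretionary stop. The documents do not support saying that the last four doses are unmonitored or that a known late liver risk is being missed.

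**What to change.** **Main change (SAP 10.4.2, before database lock).** State that unscheduled post-dose ALT, AST and bilirubin readings count in the maximum post-dose >3x, >5x and >10x ULN tables, as SAP 10.4.4 does for QTc. The combined ALT/AST and bilirubin table is defined only by timepoint, so give it an any-post-dose line on the same basis. Keep the by-timepoint tables scheduled-only, and report the number of unscheduled liver draws per arm. The cost is a text change and some programming. The downside is that subjects with a suspected rise have more readings, so the maximum is no longer purely schedule-based. The per-arm count lets a reader judge this.

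**Secondary change (Appendix A, both Parts).** Add ALT, AST, ALP and bilirubin at the existing Day 71 visit for subjects not yet past it. Blood is already drawn there for glucose, ketones and free fatty acids. The cost is about 5 mL per subject (5/404.5 = 1.2% of the Part A total in Table 7-2; 5/380.5 = 1.3% of the Part B total in Table 7-3), laboratory fees for at most about 150 panels, and a protocol amendment. SAP Section 12 shows that Part A has had its first interim look, so the gain is mainly in Part B. Day 71 needs its own denominator, because the maximum tables would otherwise mix two schedules without saying so.
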